8.9. Sample size considerations

Based on data from the NETT trial, published trials in sustained OT treatment⁵⁴, and single-dose challenge studies in autism⁴⁹ we expect our sample size (n=25/group with 5% attrition) to yield 80% power to detect a difference in means of 0.40, assuming a standard deviation of differences of 0.670, with a 0.050 two-sided significance level. Although potentially underpowered, we believe data from this trial will provide important information on safety, tolerability, and treatment targets from a novel, multi-dosing OT-combined treatment strategy. Specific Aim 2 (treatment targets, pre-treatment factors predictors). Repeated measures ANOVAs will be conducted to evaluate group differences on social behavior and social cognition composites, social recognition, mental state inference, affiliation, social reward and social competence (i.e. SSIS) in order to identify potential treatment targets for the combined treatment approach. Factors predicting treatment response will include global scores on all baseline measures. Responder status will be entered as a categorical variable as defined above (CGI-I≤2 + SSIS > 25%). PCA will be conducted on significant baseline predictors to develop composite variables and used to predict response using logistic regression.

Confidential

Rush University Medical Center

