2.1. Primary aim

To determine safety, tolerability, and efficacy of integrating OXT dosing within a CBI-SST curriculum for social cognitive impairments in ASD. Eighty youth, ages 8-11 with ASD will be randomized into 1) Integrated Oxytocin and NETT- ASD(ION-ASD) or 2) control condition (facilitated play group) to evaluate: (A) safety and tolerability of targeted, intra-nasal OXT dosing within a 12-session, CBI-SST group curriculum, and (B) group differences on dual domains associated with social learning: social behavior and social cognition. Our working hypothesis, supported by pilot data, is that ION-ASD will be associated with greater differential improvement on dual targets of social behavior and social cognition relative to the control condition.

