3.1. Study Design

This is a two-phase, 3 year, randomized, single-blind, parallel group, contact controlled pilot trial of OXT augmentation of CBI groups in youth with ASD. Phase 1 (n=10) is an initial development trial to refine manuals, procedures, and outcome evaluations. Phase 2 (n=70) will evaluate feasibility, safety, and preliminary efficacy of ION-ASD relative to the contact control (i.e. social play group). All participants are expected to be outpatients and will participate in a 12-session group therapy, with a follow-up study visit at 24 weeks. Evaluations will be conducted at four time points: Screening, Baseline, Endpoint (week 12), and Follow-up (1-month & 3-months post-treatment).

Each phase will randomly assign in a 1:1 ratio to either ION-ASD or control in blocks of 10. Efficacy outcomes will be evaluated by both caregiver report and blinded independent evaluators (IE); safety assessments will be conducted by unblinded treating medical clinicians (Medical TC). Caregivers and participants will be instructed to conceal group assignment from IEs. IEs, participants, and caregivers will also be instructed on reporting strategies should group assignment be revealed. Corrective action plans in these scenarios will be employed if necessary and include changing IE raters and flagging data. IEs will be asked to “guess” patient conditions at the end of the trial to evaluate integrity of the blind.

Medical TCs will monitor side-effects using weekly ratings with the participant and caregiver. Clinical IEs will evaluate global functioning and social communication skills. Neurocognitive IEs will conduct blinded neurocognitive assessments (see Appendix A: Time & Events Schedule).

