3.5. Randomization

This pilot study will recruit 90, youth with ASD ages 8-11 years old into a randomized, parallel group design of 1) ION-ASD and 2) control group – facilitated play. A feasibility trial will be conducted with the first 10 participants to refine the protocol including finalizing measures to support Aim 2 (brain-based behavior

Confidential

Rush University Medical Center

toolbox). If substantial protocol revisions are made, modifications to the protocol, consent, and IND will be made before proceeding with recruitment.

Participants will be randomized 1:1 to ION-ASD or control. After eligibility is confirmed and consent is obtained, eligible participants will be assigned a study randomization number according to computer-generated randomization list.

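### The 80% power stated for 25 per group fits a paired test; the planned between-arm comparison has about 54% on the same inputs, or 52% after attrition

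*Protocol*

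**What the plan says.** Protocol section 8.9 (Sample size considerations) expects "n=25/group with 5% attrition) to yield 80% power to detect a difference in means of 0.40, assuming a standard deviation of differences of 0.670", two-sided at 0.05. It names no test and does not say what the 0.670 is measured on. The next sentence concedes that the trial may lack power, but leaves the 80% in place.

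The comparison to be powered is between arms. Section 2.1 hypothesises greater improvement under ION-ASD than under control. Section 3.1 describes a parallel-group design and section 3.5 a 1:1 allocation. Section 8.8 and the SAP (Data Analysis, Primary) both fit a linear mixed model with condition, time and their interaction.

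The enrolment figures differ:

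- Section 2.1: "Eighty youth, ages 8-11 with ASD will be randomized".
- Section 3.1: Phase 1 has 10 participants, and "Phase 2 (n=70) will evaluate feasibility, safety, and preliminary efficacy of ION-ASD relative to the contact control".
- Section 3.5: "This pilot study will recruit 90, youth with ASD ages 8-11 years old into a randomized, parallel group design". Section 3.2 also gives 90.
- Section 8.9: 25 per group, which is 50 in total.

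**The concern.** An SD of differences is the input to a paired or one-sample test, where each participant supplies one difference and the variance of its mean is SD²/n. In a parallel-group comparison the two arms' mean changes are independent, so the variance of their difference is 2·SD²/n for n per arm. Using the paired formula halves that variance and overstates power.

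Efficacy is part of the primary aim. If the result is null, readers will set it against a stated 20% chance of missing a difference of 0.40. At the stated size that chance is 46% to 48%. Because 25 per group corresponds to no enrolment figure elsewhere, the protocol also has no power statement for any sample it says it will recruit.

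**Working it through.** **Inputs.** From section 8.9: difference δ = 0.40, SD = 0.670, two-sided α = 0.05, 25 per group, 5% attrition (25 × 0.95 = 23.75, about 24). From sections 3.1 and 3.5: independent arms, 1:1. The standardised difference is 0.40/0.670 = 0.597. Power comes from the noncentral t distribution.

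**Step 1: reproduce the stated 80%.** For a paired or one-sample t-test, the noncentrality is (δ/SD)·√n with n − 1 degrees of freedom.

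- n = 24: 0.597 × √24 = 2.92, power 79.98%.
- n = 25: 0.597 × √25 = 2.99, power 81.7%.

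The stated figure is returned at the number left after the stated attrition.

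**Step 2: the comparison the trial makes.** For a two-sample t-test on change scores, the noncentrality is (δ/SD)·√(n/2) with 2n − 2 degrees of freedom, n being the number per arm.

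- n = 25: 0.597 × √12.5 = 2.11, power 54.3%.
- n = 24: 2.07, power 52.6%.
- n = 23.75: 2.06, power 52.1%.

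The normal approximation gives 56.0% at 25. A one-sided test would give 67% to 68%, but the section specifies two-sided. For 80% the t-test gives 79.98% at 45 per arm and passes 80% at 46. With 5% attrition, 46/0.95 = 48.4, so 49 enrolled per arm.

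**Step 3: the enrolment totals given elsewhere.** Same δ, SD and α, two-sample t-test:

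| Total N | Per arm | Power | Per arm after 5% attrition | Power | Detectable difference at 80%, before / after attrition |
|---|---|---|---|---|---|
| 50 (section 8.9) | 25 | 54% | 23.75 | 52% | 0.54 / 0.56 |
| 70 (section 3.1, Phase 2) | 35 | 69% | 33.25 | 67% | 0.46 / 0.47 |
| 80 (section 2.1) | 40 | 75% | 38 | 73% | 0.42 / 0.44 |
| 90 (sections 3.2, 3.5) | 45 | 80% | 42.75 | 78% | 0.40 / 0.41 |

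**Step 4: could 80% at 25 per arm be right on another reading?**

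- An SD of individual change of about 0.49 would be needed, against the stated 0.67.
- If 0.670 were √2 times a per-participant SD, that SD would be 0.670/1.414 = 0.474. Two-sample power would then be 81.3% at 23.75, 81.7% at 24 and 83.3% at 25. Nothing in the documents gives the 0.670 this meaning.
- Baseline adjustment (ANCOVA) is not the planned model. If 0.67 is the SD of change and the baseline-to-endpoint correlation is ρ, it replaces 0.67 by 0.67·√((1+ρ)/2). For assumed ρ of 0.3, 0.5, 0.7 and 0.8, power at 25 per arm is 73%, 67%, 61% and 59%, still short of 80%.

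**The case against.** The strongest reply has four parts.

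- **The test is inferred.** Section 8.9 names no test, and the sources for the 0.670 cannot be seen. The √2 reading in Step 4 gives 81% to 83%, so a paired test is not the only route to roughly 80%. This stands in part: the paired reading is likely, not proven. But the √2 reading is unusual in an unpaired design and has no support in the text.
- **The 54% belongs to a size no other section plans.** At 70 to 90 participants the chance of missing a difference of 0.40 is about 20% to 33%. This is correct, and the 54% should be read as the power at 25 per group, not necessarily at final enrolment. It does not rescue the statement, which attaches 80% to 25 per group; only 90 comes near 80%, and only before attrition.
- **The trial is a pilot with open caveats.** Section 8.9 concedes possible low power, and section 8.8 and the SAP both warn that wide confidence intervals may prevent firm conclusions. These limit the harm, but a general caution beside a specific 80% leaves the reader unable to tell which governs.
- **A t-test on change scores is only a proxy.** The planned model is a mixed model over several visits with covariates examined. This stands as a limit on precision; the proxy should be labelled as one.

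The 80 and 90 might also be partly explained as randomised versus recruited, but section 3.5 recruits the 90 into the randomised design, so its wording does not settle this.

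**Conclusion.** The stated power is wrong as written. On section 8.9's own inputs the between-arm comparison has 54% power at 25 per arm and 52% after 5% attrition, roughly 26 to 28 percentage points below the claim. It would need 45 to 46 evaluable per arm for 80%. At totals of 70, 80 and 90, power is 69%, 75% and 80%, or 67%, 73% and 78% after attrition.

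These figures assume that 0.67 is the SD of individual change, and that a two-sample t-test stands in for the condition-by-time contrast. That the authors used a paired formula is a strong inference from the wording and the near-exact match at 24. The shortfall does not depend on how the 80% arose. Because this is the protocol's only power statement, it must be corrected.

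**What to change.** In section 8.9, delete the claim of 80% at 25 per group. Replace it with a calculation for two independent groups on change scores that:

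- names the test and says it approximates the mixed-model contrast;
- states what the 0.670 is the SD of;
- reports power or the detectable difference after the 5% attrition.

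Use one N throughout sections 2.1, 3.1, 3.2, 3.5 and 8.9, and say whether the 10 Phase 1 participants enter the efficacy analysis. If they do and 80 are randomised, the text could read: with 40 per arm and 5% attrition, 73% power for a between-arm difference of 0.40 (SD of change 0.67), and a detectable difference of about 0.44 at 80% power. If efficacy rests on Phase 2 alone (70), the figures are 67% and about 0.47. If 90 are randomised, they are 78% and about 0.41.

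The cost is rewriting one paragraph and aligning the enrolment figures. Design, treatment and data collection are unchanged and no added recruitment is required. The stated power becomes less favourable.

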Results: NETT participants improved on the social behavior composite capturing nonverbal communication, social relations, and empathic responding skills at endpoint compared to controls ($B=-.31$, $SE=.14$, $p=.04$). No group differences were found on the social cognition composite ($B= 0.00$, $SE=.13$, $p=.98$). Outcomes at a three-month follow-up interval were not significant suggesting a potential waning effect of the CBI intervention over time ($B=-.14$, $SE=.19$, $p=.47$). Moderator analyses indicated higher verbal IQs were associated with social behavior improvements in NETT but not controls ($B=-.02$, $SE=.01$, $p=.03$). Results also show improvements on low-intensity (i.e. more ambiguous) facial emotion identification items in NETT but not controls (estimate =1.1, $p<.01$, Cohen's $d = .56$). Poor quality data and compliance issues limited the imaging sample to approximately

Confidential

Rush University Medical Center

half of the behavioral data. In this subset of participants, NETT increases activation in mentalizing regions including the medial prefrontal cortex and temporal pole junction during an averted eye gaze task (Figure 2)⁵⁰.

Summary: Our findings demonstrate short-term, specific treatment effects of targeted CBI-based SST curricula of NETT on core social-communication behaviors in youth with ASD. The limited effects on social cognitive processes are supported by two recent Cochrane reviews^{14,51}.

Intranasal oxytocin for the treatment of children and adolescents with autism spectrum disorder

ClinicalTrials.gov lists 22 clinical studies of intranasal oxytocin (IN-OXT) in ASD which are actively or recently completed recruitment. Of the handful of published findings in this area, the vast majority include small single-dose challenge studies in adults with ASD. Studies suggest a medium effect size on measures of social cognition and social impairment⁴¹. Overall, IN-OXT was well-tolerated and had a side effect profile including restlessness, increased energy, and increased irritability. The PI and collaborators published on a modified maximum dose-finding and safety study of a 12-week oxytocin daily monotherapy in verbal, youth with ASD⁵². The highest dose evaluated was .4 IU/kg/dose and was well-tolerated. Several measures of social behavior, repetitive behavior, and social cognition demonstrated change at endpoint (12 weeks) as well as at a 3-month follow-up post-discontinuation of IN-OXT⁴⁰.

2. Study Aims

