8.8. Statistical analysis

Specific Aim 1 & Exploratory Aim 1: Safety and tolerability will be analyzed by analyzing for group differences on total scores and domains of the AE form and satisfaction surveys respectively. Efficacy analysis will be follow analytic procedures used to derive social behavior and social cognition composites for the Seaver-NETT RCT¹⁶. First, a principal components analysis with varimax (orthogonal) rotation will be conducted on subscales of the primary social behavior measures - Griffith Empathy Scale and CCC-2; and raw total scores on primary social cognition outcomes – RMET and DANVA2. The PCA is used to develop composite scores in a field with no viable outcomes for higher-order core social impairments as well as to minimize floor and ceiling artifacts, effects of variability in response, and other sources of measurement error. Variables with high factor loadings for subscales will be entered into composite score development for the social cognition and social behavior composites. Missing, invalid, and/or incomplete data (i.e. more than 30% items missing when not pre-defined by scale) will be excluded from the factor analysis.

A linear mixed model analysis will be conducted on all participants with at least two of four available time points (Wk 0, Wk 12, 1-mon, 3-mo). Composite scores of co-primary outcomes social behavior and social cognition will be used as the response variable; treatment condition, time, and condition * time interactions will be covariates. Verbal IQ will also be entered into the model in exploratory moderator analyses. We will estimate effect sizes (Cohen's d) and confidence intervals (95%) acknowledging the likelihood that analyses may not permit definitive conclusions given the likely size of the confidence intervals.

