Data Analysis. Primary: Composite scores of both primary outcomes (i.e., SBI and SC) will be used as the response (i.e., outcome) variable in a series of mixed-effects linear regression models using the *lmer* package in *R Studio* to assess the effect of treatment condition (ION-ASD vs. Facilitated Play), time (e.g., change from baseline after 12 weeks), and condition X time interaction. Across all models, the individual participant will be included as the random effect. Age, verbal IQ, ADHD and generalized anxiety (from the Child & Adolescent Symptom Inventory-5 [CASI-5] T-scores) will be entered into the model to be examined as potential covariates and/or moderators to outcomes as in prior work. We will estimate effect sizes (standardized Betas) and confidence intervals (95%) acknowledging the likelihood that analyses may not permit definitive conclusions given the likely size of the confidence intervals. Finally, if the statistical assumptions of the model are not met (e.g., homoscedasticity, normality, linear relationships), generalized linear models with appropriate link functions or potential transformations of predictor variables will be assessed.

Secondary Outcomes. The linear mixed-effects models will also be used on secondary outcome measures: SRS T-score, mean Caregiver Strain Global rating scale. Responder (i.e., Clinical Global Inventory-Improvement [CGI-I]) analysis will be conducted using either a Chi-squared or Fisher's exact test (when observations are small such that $>20\%$ of cells have *expected* count <5) on the number of responders (i.e., CGI-I scores of 1-2) versus non-responders (i.e., CGI-I scores of 5-7) by group.

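### Aim 2 analyses the primary composites a second time, and the task outcomes and SSIS for the only time, by repeated-measures ANOVA with no visits named, although a mixed model is already specified

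*Protocol*

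**What the plan says.** Protocol section 8.9, in its text on Specific Aim 2, states: "Repeated measures ANOVAs will be conducted to evaluate group differences on social behavior and social cognition composites". The same sentence adds the task domains (recognition, inference of mental states, affiliation, reward) and social competence on the SSIS. It does not name the visits that enter, and it gives no rule for missing visits.

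The two composites already have a method. Protocol section 8.8 states: "Composite scores of co-primary outcomes social behavior and social cognition will be used as the response variable", and "A linear mixed model analysis will be conducted on all participants with at least two of four available time points". The four time points are week 0, week 12, and one and three months after treatment. The SAP also fits mixed-effects models to both composites, with condition, time and their interaction, and says: "Across all models, the individual participant will be included as the random effect". It then extends them: "The linear mixed-effects models will also be used on secondary outcome measures: SRS T-score, mean Caregiver Strain Global rating scale". The SAP mentions neither repeated-measures ANOVA, nor the Aim 2 tasks, nor the SSIS.

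Protocol section 5.2, under the termination visit, asks children who withdraw to complete the endpoint procedures at their last visit, so that an intention-to-treat analysis is possible.

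**The concern.** Two methods are planned for the same two composites, and they can use different children. The mixed model keeps any child with two time points. Classical repeated-measures ANOVA keeps only children observed at every visit entered. If weeks 16 and 24 enter, a child who withdraws after giving endpoint data stays in the mixed model and is lost from the ANOVA, which works against the purpose of the termination visit. The SAP's cleaning rules remove single observations (missing items, too few responses, some outliers). In an ANOVA on a composite, one removed observation takes the whole child out.

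At stake are a second result for each primary outcome that may disagree with the first, lower precision for the task outcomes and the SSIS, and bias if missing visits depend on how a child is doing.

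**Working it through.** **Inputs**

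- Children per arm: 35, from 70 in Phase 2 at 1:1 (Protocol 3.1). Other totals appear: 80 in 2.1, 90 in 3.5, 25 per group in 8.9. The percentages below do not depend on this choice.
- Baseline: treated as complete, because Protocol 5.2 has the randomization form opened after the baseline assessments.
- Missed visits: the documents give only 5% attrition (8.9). Rates per visit of 5%, 10% and 15%, and independence between visits, are assumptions.
- Difference 0.40, standard deviation 0.670, two-sided 0.05 (8.9), used only to put the losses on a power scale.

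**The plan's own figure.** None is given for the ANOVAs. The 80% power in 8.9 reproduces as a paired t-test: with n = 24 (25 less 5%), noncentrality (0.40/0.670) × √24 = 2.92 on 23 degrees of freedom gives 80.0%. As a comparison of two groups of 24 it gives 53%. That is a separate matter and is not relied on here.

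**Children kept.** Let m be the chance of missing a visit and k the number of post-baseline visits entered.

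- ANOVA: (1 − m)^k.
- Two-of-four rule, baseline complete: 1 − m³, since one of the three later visits is enough.

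ANOVA power uses the noncentral t with 2n − 2 degrees of freedom and noncentrality (0.40/0.670) × √(n/2), where n is the number kept per arm.

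| Case | ANOVA keeps | Of 35 per arm | Mixed model keeps | ANOVA power |
|---|---|---|---|---|
| Baseline and week 12 only, 5% missed | 0.95 = 95% | 33 | 95% on the same two visits | 67% |
| 5% pure dropout, any visits | 95% | 33 | 95% to 100%, by whether they leave before or after week 12 | 67% |
| Three later visits, 5% each | 0.95³ = 86% | 30 | 99.99% | 62% |
| Three later visits, 10% each | 0.90³ = 73% | 26 | 99.9% | 55% |
| Three later visits, 15% each | 0.85³ = 61% | 21 | 99.7% | 48% |

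With all 35 per arm observed, power would be 69%. This is an upper bound for the mixed model, because children with gaps contribute less than full information.

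**Bias, by illustration.** In 200 simulated trials with 35 per arm and a true week-12 effect of 0.40, week 12 was missed at random by 5%, and later visits were missed more often by children with less gain at week 12. About 26% of children were incomplete. The complete-case estimate averaged 0.34 and the mixed-model estimate 0.39 (Monte Carlo standard error about 0.013). When missingness did not depend on gain, both averaged about 0.42. The dependence was chosen for illustration, not estimated from the documents.

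**The case against.** The strongest reply is that a baseline-to-week-12 ANOVA is a fair reading. Protocol 2.2 frames Aim 2 as change following treatment. Durability at one and three months is a separate exploratory aim (2.3), which 8.8 covers with the mixed model. On that reading few children are lost. This stands, and it limits the size of the point. It does not settle it: Appendix A schedules the SSIS, RMET, DANVA2, TAT and biological motion task at baseline and weeks 12, 16 and 24, so a four-visit ANOVA is also natural. The trustworthiness and trust-game tasks are not named in that schedule, so four visits for affiliation and reward would be an assumption.

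It can also be said that the SAP analyses the composites only by mixed model, so a second result rests on the protocol alone. That is true, but the SAP does not withdraw the ANOVAs and leaves the tasks and SSIS with no other method.

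Three stronger readings are tempting and are not supported:

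- A reader might infer that the plan discards every child who misses any visit. No document says so. It is how the classical method behaves for whichever visits are entered, and these are not named.
- A reader might take "Poor quality data and compliance issues limited the imaging sample to approximately" half of the behavioural data (Protocol 1.1) as a forecast for the Aim 2 tasks. That loss was in fMRI, with the behavioural data as the larger reference set. Aim 2 uses computer and eye-tracker tasks and a caregiver form.
- A reader might raise the retention rate to the fourth power, giving 81%, 66% and 52%. That lets baseline be missing, although randomization follows the baseline assessments.

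**Conclusion.** The point holds as an inconsistency of method in a secondary aim of a pilot. The composites are assigned two analyses with potentially different analysis sets, and the task outcomes and SSIS are left with the weaker one.

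Its size is conditional. About 5% of children are lost if only baseline and week 12 enter with 5% missed, or if the 5% attrition is pure dropout. About 14%, 27% or 39% are lost if three post-baseline visits enter and are missed independently at 5%, 10% or 15%. Independence is the unfavourable case, since losses from leaving the study overlap across visits.

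The mixed model reduces the loss of precision, and reduces bias if data are missing at random. It removes neither entirely: loss driven by unobserved behaviour or tolerability may not be missing at random, and the two-of-four rule still drops children with a single time point. The primary analysis is unaffected.

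**What to change.** In Protocol 8.9 and the SAP, replace the ANOVAs with the mixed model with a participant random effect (condition, time, condition-by-time) for all continuous Aim 2 outcomes, including the tasks and the SSIS. State that time is categorical, which neither document now says. Name the visits that enter for each outcome. For the two composites, cite the primary mixed-model result instead of testing them again.

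The cost is wording in two documents and a little analysis work to apply the existing model to more outcomes. No new data are needed.

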2.2. Secondary aim

To evaluate the sensitivity of candidate tasks to refine treatment targets and identify predictors of treatment response from ION-ASD. The long-term goal of this aim is to support development of a brain-based behavioral toolbox for use in future intervention research on social learning in youth with ASD. The goals in this proposal will investigate 1) putative treatment targets associated with change following ION-ASD and 2) pre-treatment factors predictive of response to ION-ASD. We predict treatment response in ION-ASD, as defined by a clinical global impression improvement score of <2 (improved to very much improved, and 25% improvement on the Social Skills Improvement System (SSIS), will be associated with improvement on candidate tasks of social-emotional perception, attention to eye region, mental state attributions, and affiliation.

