4.2. Efficacy Assessments

Efficacy assessments will be evaluated through questionnaires, direct assessments of social cognition, and questionnaires surveying quality of life, social functioning, anxiety, & repetitive behaviors.

Primary Outcome Measures. This study has two primary outcomes reflective of the dual treatment targets to underlie social learning in school-age children: social cognition and social behavior. Each outcome will be measured by a composite score developed through a factor analysis of measures in each domain in the Seaver-NET RCT¹⁶.

1. Social Behavior Composite. (Baseline, Week 12, Week 16, Week 20)
 - a. *Children's Communication Checklist (CCC)*⁵⁵. The CCC⁵⁵ is a 70-item caregiver rating scale which includes language scales (e.g. speech, syntax) and pragmatic scales (e.g. scripted language, nonverbal communication, social relations).
 - b. *Griffith Empathy Scale*.⁵⁶ The Griffith Empathy Measure⁰ is a 23-item caregiver rating scale that assesses both affective and cognitive empathy in children and adolescents. The measure was adapted from Bryant's Index of Empathy³² by Dadds and colleagues.
2. Social Cognition Composite (Baseline, Week 12, Week 16, Week 20)
 - a. *Reading Mind in Eyes Test (RMET)*. The RMET examines an individual's ability to determine what a person is thinking or feeling based on photographs of the eye region of male and female faces. A computerized, combined child and adult version of the RMET will be used in the trial reflecting clinical measurements employed in a larger, NIH-funded monotherapy trial of oxytocin vs. placebo⁵⁷.
 - b. *Diagnostic Analysis of Nonverbal Accuracy-2 (DANVA2)*⁵⁸. The DANVA2 examines emotion recognition using both visual and auditory stimuli. Participants were administered all subtests of the DANVA2.

Secondary Outcome Measures. While functional improvements are not expected to be clinically significant within the brief intervention, we will assess changes in social and quality of life metrics as secondary outcomes with the following measures.

1. Global functioning

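### The Aim 2 predictor analysis has no treatment-arm contrast, so it cannot tell factors that predict benefit from ION-ASD from factors that predict improvement in either arm

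*Protocol*

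**What the plan says.** Protocol section 2.2 sets the goal as identifying "pre-treatment factors predictive of response to ION-ASD".

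Section 8.9 gives the method. "Factors predicting treatment response will include global scores on all baseline measures". Then: "PCA will be conducted on significant baseline predictors to develop composite variables and used to predict response using logistic regression". No arm variable, interaction or analysis population is stated for these steps.

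Response is defined in three places, in three ways:

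- Protocol 2.2: "clinical global impression improvement score of <2 (improved to very much improved, and 25% improvement on the Social Skills Improvement System (SSIS".
- Protocol 8.9: "Responder status will be entered as a categorical variable as defined above (CGI-I≤2 + SSIS > 25" percent.
- SAP, Secondary Outcomes: CGI-I 1 to 2 against CGI-I 5 to 7. There is no SSIS component, and scores of 3 and 4 fall in neither class.

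The control arm is used in neighbouring analyses. For the treatment-target half of Aim 2, section 8.9 says "Repeated measures ANOVAs will be conducted to evaluate group differences on social behavior and social cognition composites", and its list of measures includes the SSIS. The SAP compares CGI-I responders between arms. It also examines age, verbal IQ, ADHD and generalized anxiety as possible covariates or moderators, but in models of the two composites, not of responder status. Protocol 8.8 likewise adds verbal IQ to the composite models as an exploratory moderator. The SAP contains no Aim 2 predictor analysis.

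**The concern.** A predictor of response to a treatment is a factor whose relation to outcome differs between the treated and control arms. A factor with the same relation in both arms is prognostic: it marks children who improve for any reason, such as maturation, retest effects or general group contact. Without a contrast between arms the two cannot be told apart.

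The facilitated play arm exists to supply that contrast. Section 1.1 describes its role in the previous trial as a control for time, therapist training, peer exposure and parent engagement. It also reports that trial's verbal IQ moderator as present in the active arm and absent in controls. Section 8.9 does not ask for the same contrast here.

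Aim 2 is meant to inform the choice of targets and predictors for later trials. A prognostic factor carried forward as a predictor of ION-ASD response could steer eligibility or enrichment in those trials towards children who would have improved anyway.

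**Working it through.** **Plan's own figure.** The only computed figure in 8.9 is 80% power for a mean difference of 0.40 with SD 0.670. A one-sample (paired) t calculation with n = 24 (25 × 0.95 = 23.75, rounded up) gives 0.800. The same inputs as a two-group t comparison give 0.526. Neither figure bears on the predictor analysis, for which the plan gives no number.

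**What each model tests.** Let X be a baseline score, T the arm (1 = ION-ASD) and Y response, with

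logit P(Y = 1) = a + bX + cT + dXT.

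- ION-ASD only: the slope on X is b + d.
- Arms pooled, no arm terms: with 1:1 allocation the slope is roughly b + d/2.
- Both arms with interaction: the test is on d alone.

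Section 2.2 asks about d. A purely prognostic factor has b ≠ 0 and d = 0, so either of the first two analyses can be significant when the answer to the aim's question is no.

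**Inputs.** The sample size range comes from the protocol: 25 per group (8.9), 35 per arm in Phase 2 (70/2, section 3.1) and 40 per arm (80/2, section 2.1). Sections 3.2 and 3.5 give 90, or 45 per arm. That was not run; a larger sample raises the first two rates. Response rates and strengths of association are assumptions, because the documents give none.

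**Chance that a purely prognostic factor is declared a predictor** (simulated logistic regressions, likelihood-ratio test at 0.05):

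| Assumptions | ION-ASD only | Pooled | Interaction |
|---|---|---|---|
| 25–40 per arm, 10–40% respond, correlation 0.3–0.5 with improvement in both arms | 17–77% | 25–97% | 5–10% |
| 25 per arm, 20–40% respond, odds ratio 2–3 per SD in both arms | 29–64% | 45–87% | 7–8% |
| 35 per arm, same | 37–79% | 59–97% | 6–7% |

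In the first row, the low ends for the two analyses without an interaction come from 25 per arm, 10% responders and correlation 0.3. The high ends come from 40 per arm, 40% responders and correlation 0.5. The interaction test runs slightly above its nominal 5% at these sizes.

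**Power of the interaction test.** For a strong true moderator (odds ratio 3 in ION-ASD, 1 in control; 40% responding in ION-ASD, 20–30% in control), power is about 35% at 25 per arm and 44–48% at 35 per arm.

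**Multiplicity.** Appendix A lists 16 parent or participant measures at baseline, or 18 with the two given only at screening. If all were null and independent, the chance of at least one significant at 0.05 is 1 − 0.95^16 = 0.56 to 1 − 0.95^18 = 0.60.

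**Responder definitions.** In 2.2, a CGI-I below 2 admits only a score of 1, yet the gloss beside it describes a wider range and 8.9 admits 1 and 2. A child with CGI-I 2 and a 30% SSIS gain is a responder under 8.9 and the SAP, but not under the literal cut-off in 2.2. A child with CGI-I 2 and a 10% SSIS gain is a responder under the SAP only. A child with CGI-I 3 is a non-responder under the protocol and unclassified under the SAP.

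**The case against.** The strongest reply is that section 8.9 is silent on arms; it does not prescribe an analysis of ION-ASD alone. That is correct, and the point is one of under-specification. It matters because both natural readings of the text, ION-ASD alone or arms pooled, give the same misinterpretation.

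A reader might go further and infer that natural improvement could be reported as treatment response in the trial generally. The documents do not support that. The SAP compares CGI-I responders by group, and 8.9 tests group differences on the SSIS, so improvement common to both arms would show in the control arm.

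A reader might also take the remark in 4.2, "While functional improvements are not expected to be clinically significant within the brief intervention", to mean that any response seen must be natural improvement. It does not follow. CGI-I and SSIS are both listed under that remark, but low expected change points to few responders and unstable models, not to misattribution. Nor does the remark state a response rate.

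It can also be said that this is a secondary aim of a pilot, that 8.9 concedes possible low power, and that 8.8 warns against definitive conclusions. The SAP does examine four moderators in two-arm models of the composites. All of this stands and limits the weight of the point, but none of it covers the responder model. The 2.2 cut-off may be a lost underline, since its own gloss and 8.9 agree with each other. The difference from the SAP definition would remain.

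**Conclusion.** The point holds for the Aim 2 predictor results only. As written, section 8.9 cannot answer the question posed in 2.2, and the SAP does not fill the gap. The rates in the table rest on assumed response rates and associations and should be read as ranges. The ordering does not depend on the exact inputs: in every setting tried, the two analyses without an interaction flag a purely prognostic factor far more often than the interaction test does. The three responder definitions are a separate, smaller inconsistency, but they decide who counts as a responder in this same analysis. Because the contrast uses data already scheduled in both arms, the change should be made; it does not affect the primary analysis.

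**What to change.** In protocol 8.9, with a matching paragraph in the SAP:

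1. State the analysis population as both randomized arms.
2. Test each candidate predictor by its interaction with treatment condition in a model that also contains the arm and the predictor. Describe main effects as prognostic only.
3. Label all predictor results exploratory, and report interaction estimates with confidence intervals.
4. Reconcile the responder definitions in protocol 2.2, protocol 8.9 and the SAP into one. Settle the CGI-I cut-off, whether SSIS is required, whether exactly 25% counts, and how CGI-I 3 and 4 are classed.

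Optionally, add a supportive analysis of continuous change in the SBI and SC composites with the same interaction, since few children may meet the responder definition. Replacing the aim's own response variable is not necessary.

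The cost is wording in two documents and no new data: Appendix A schedules the baseline measures, CGI-I and SSIS without restriction by arm. The downside is power of about 35–48% even for a strong moderator at 25–35 per arm. Fewer predictors will be claimed, and a null interaction will not rule one out.
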